4.2.5 Per Protocol set

The Per Protocol set (PP) will consist of all randomized subjects who receive at least one dose of the IMP without any Major Protocol Deviations. The PP set will be used for sensitivity analyses.

All the protocol deviations will be discussed case by case by the clinical team during the Data Review Meeting (DRM) before the database lock and described in the DRM Report.

4.3 Usage of analysis sets

The usage of the analysis sets (see previous section) for the creation of tables and figures are illustrated in Table 3

Table 3: Usage of analysis set

Analysis	ENR	RND	FAS	SAF	PP
Subject enrolment and disposition	X				
Protocol violations		X			
Study discontinuations		X			
Patient status		X		X	
Demographics and baseline characteristics			X		
Medical/Surgical History and Concomitant Diseases			X		
Prior and concomitant medications			X		
Other baseline characteristics			X		
Treatment information				X	
Exposure to IMP				X	
Analysis of primary efficacy endpoints			X		
Sensitivity analysis			X		X
Analysis of secondary efficacy endpoints			X		
Analysis of exploratory efficacy endpoints			X		
Adverse events				X	
Clinical laboratory evaluation				X	
Vital signs				X	
Pregnancy test over the study				X	

Unless otherwise specified, all listings will be done for RND set. All listings will report:

- planned and actual treatment names included,
- the flag(s) of the analysis set(s) used to analyze the information in the listing (according to Table 3).

4.4 Sub-group analyses

Statistical tests for interaction (between subgroup and treatment arm) will be performed to decide about the need to further investigate subgroups of the trial population. The consistency of the treatment effect will be assessed using a Cox regression model including treatment, subgroup variable and their interaction as covariate.

The following subgroups will be defined based on demographic or baseline characteristics:

- age group (≤ 65 yrs vs > 65 yrs);
- gender (Male, Female);
- clinical severity score at baseline ($<$ median vs \geq median);
- dyspnea VAS scale at baseline ($<$ median vs \geq median).

Subgroup analysis will be performed if interaction tests are statistically significant at 15% nominal level. In this case all efficacy endpoints will be analyzed within as described in sections 7.1.2, 7.2.1 and 7.2.2.

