### - Phase 2/3 Study Endpoints:

- **Primary Endpoint for Phase 2:** Composite endpoint of clinical events (the patient requires at least one of the following: supplemental oxygen requirement, mechanical ventilation use, admission to ICU, and use of a rescue medication for any reason)
- **Primary Endpoint for Phase 3:** Composite endpoint of death and clinical severe events (the patient dies or requires mechanical ventilation use and/or admission to ICU)
- Secondary Endpoints:
  - Changes in clinical severity score (as recommended by WHO for COVID studies), defined as the time to clinical improvement of two points from the time of randomization on a seven-category ordinal scale or live discharge from the hospital, whichever comes first. The seven-category ordinal scale consists of the following: 1) not hospitalized, with resumption of normal activities; 2) not hospitalized, but unable to resume normal activities; 3) hospitalized, not requiring supplemental oxygen; 4) hospitalized, requiring supplemental oxygen; 5) hospitalized, requiring high-flow oxygen therapy, noninvasive mechanical ventilation, or both; 6) hospitalized, requiring ECMO, invasive mechanical ventilation, or both; and 7) death.
  - Dyspnea severity (Liker scale and VAS scale)
  - Changes in body temperature
  - Changes hematology test values
  - o Duration and quantity of supplemental oxygen treatment
  - Incidence and duration of mechanical ventilation use
  - o Incidence of intensive care unit (ICU) admission need
  - Lung damage extension changes from baseline (assessed by Chest CT or Rx)
  - Change from baseline in lung exudation degree (assessed by Chest CT or Rx)
  - o PaO2
  - o SpO2
  - Partial arterioral oxygen pressure (PaO2) to fraction of inspiration O2 (FiO2) ratio
  - o CRP
  - o Hs-CRP

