#### 5.2 Inclusion/exclusion criteria

#### Phase 2 Inclusion Criteria:

- 1. Age 18 to 90.
- 2. Confirmed COVID-19 diagnosis
- At least one of the following: ① Respiratory distress, RR ≥ 30 breaths/min without oxygen; ② Partial arterial oxygen pressure (PaO2) / Fraction of inspiration O2 (FiO2) >100 <300mmHg (1mmHg = 0.133kPa).

- 4. Chest imaging confirms lung involvement and inflammation.
- Inflammatory status as documented by at least one of the following: Lactate dehydrogenase (LDH) > normal range, C-reactive protein (CRP) ≥ 100mg/L or IL-6 ≥ 40pg/mL, serum ferritin ≥ 900ng/mL, XDP >20mcg/mL.

Phase 3 Inclusion Criteria: same as above; other criteria TBD based on Phase 2 outcomes.

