3.5 Efficacy endpoints

3.5.1 Primary endpoints

- Primary Endpoint for phase 2: Composite endpoint of clinical events (the subject requires at least one of the following: supplemental oxygen requirement, invasive mechanical ventilation use, admission to ICU, and use of a rescue medication for any reason);
- Primary Endpoint for phase 3: Composite endpoint of death and clinical severe events (the subject dies or requires invasive mechanical ventilation use and/or admission to ICU).

3.5.2 Secondary Endpoints:

- Clinical severity score (a seven-category ordinal scale) at any available time point
- Dyspnea severity (Liker categorical scale and VAS continuous scale) at any available time point;
- Changes in body temperature at any available time point;
- Duration and quantity of supplemental oxygen treatment at any available time point;
- Incidence and duration of mechanical ventilation use at any available time point;
- Incidence of ICU admission need at any available time point;
- Lung damage extension changes from baseline (assessed by Chest CT or Rx) at any available time point;
- Change from baseline in lung exudation degree (assessed by Chest CT or Rx) at any available time point;
- PaO₂ at any available time point;
- SpO₂ at any available time point;
- Partial arteriolar oxygen pressure (PaO₂) to fraction of inspiration O₂ (FiO₂) ratio at any available time point;
- CRP at any available time point;
- Hs-CRP at any available time point;

3.5.3 Exploratory Endpoints (not mandatory):

- Cytokine profile at any available time point;

- Concentration of reparixin in serum over time;
- SARS-CoV-2 virologic counts at any available time point.

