4.7 Study adaptation

REPAVID-19 trial's design will allow for adaptations based on results from efficacy and safety data through the study. The spectrum of possible adaptations for the phase 3 study segment with the corresponding trigger rules is reported in Table 6.

In case of decision of continuation of the study, results of the phase 2 portion of study will be submitted to the competent authority with the final version of the Phase 3 segment of the study (as an amendment to study protocol) prior to proceed. In that case, the SAP will be updated accordingly.

Table 6: Adaptations and triggers

Action	Trigger
Modification of the experimental treatment route of administration.	Safety reasons based on DMC recommendation or Sponsor evaluation.
Confirmation or modification of the primary, secondary and exploratory endpoints (at beginning of phase 3).	DMC indication based on review of phase 2 results.
Refining the sample size.	In case of relevant discrepancies between sample size assumptions (section 3.2) and phase 2 results.
Population enrichment.	Based on safety and efficacy results (including subgroup analyses), it may be identified a subset of subjects most likely to benefit from treatment.
Change the allocation ratio of subjects to trial arms.	Safety and ethical reasons based on DMC recommendation or Sponsor evaluation.

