4.9 Changes in the planned analysis

No change has been implemented in this SAP.

However, in order to clarify the analysis of the primary endpoint, a clarification of the meaning of "supplemental oxygen treatment" is provided: since all patients enrolled in this study had a respiratory distress, it is intended in all the analysis that the term "supplemental" refers to additional and/or increased oxygen requirement as compared to the baseline. In fact, all patients were expected to be already on oxygen treatment before the start of treatment. Details are provided in section 9.1.

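### The median split of the baseline severity score in SAP 4.4 leaves its lower subgroup empty if more than half of patients score 4 and none score lower

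*SAP*

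**What the plan says.** SAP 4.4 lists four subgroup variables. Age and gender have fixed categories. Dyspnea VAS and the clinical severity score are split at the sample median, the latter as "clinical severity score at baseline ($<$ median vs \geq median". Each variable is tested in a "Cox regression model including treatment, subgroup variable and their interaction as covariate", and the result acts as a filter: "Subgroup analysis will be performed if interaction tests are statistically significant at 15% nominal level". The section has no rule for ties at the median or for an empty group.

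SAP 3.5.2 describes the variable as "Clinical severity score (a seven-category ordinal scale) at any available time point". Protocol section 3 defines its categories. Scores 1 and 2 are patients out of hospital, 3 is in hospital without oxygen, 6 is invasive ventilation or ECMO, and 7 is death. The two categories that matter most here are "4) hospitalized, requiring supplemental oxygen; 5) hospitalized, requiring high-flow oxygen therapy, noninvasive mechanical ventilation, or both".

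SAP 4.9 says that "all patients were expected to be already on oxygen treatment before the start of treatment". One entry route in Protocol 5.2 is nevertheless "Respiratory distress, RR ≥ 30 breaths/min without oxygen".

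On the use of subgroup results, the population enrichment row of SAP Table 6 reads: "Based on safety and efficacy results (including subgroup analyses), it may be identified a subset of subjects most likely to benefit from treatment".

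**The concern.** A split at the median suits a variable with many distinct values. Here eligibility leaves few. Every patient is in hospital, so scores 1 and 2 cannot occur. Score 3 is not expected, given SAP 4.9. Score 6 is unlikely, because exclusion criterion 7 requires a condition compatible with oral dosing; any such patient would normally fall in the upper group anyway. That leaves mainly 4 and 5.

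On a scale with two occupied values, the median is usually one of those values. Ties go to the upper group, so a median of 4 puts everyone there. The intended comparison of less severe with more severe patients then does not exist. Severity is one of only four pre-specified effect modifiers. If the rule fails, either the test is dropped or someone chooses a new cut after seeing the data.

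**Working it through.** The documents give no baseline score distribution, median or subgroup size, so there is no stated figure to reproduce. The check applies the SAP rule to possible score distributions. Inputs from the documents are 48 patients in phase 2, randomised 2:1 (32 reparixin, 16 control), and the rule that a score below the median is the lower group. The shares at each score are assumptions.

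**Step 1: what the rule does when all 48 score 4 or 5.**

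| At score 4 | At score 5 | Median | Lower group | Upper group |
|---|---|---|---|---|
| 23 | 25 | 5 | 23 | 25 |
| 24 | 24 | 4.5 | 24 | 24 |
| 25 | 23 | 4 | 0 | 48 |
| 34 | 14 | 4 | 0 | 48 |

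Moving one patient from an even split changes the groups from 24 and 24 to 0 and 48. With an empty lower group, the indicator for that group and its product with treatment are both zero for everyone. The design matrix (treatment, subgroup, interaction) has rank 1 instead of 3, and the interaction cannot be estimated.

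**Step 2: how likely that is.** Let X be the number scoring 4, with X ~ Binomial(n, p). The lower group is empty when X > n/2, that is X ≥ 25 for n = 48.

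| Assumed share at score 4 | P(lower group empty), n = 48 |
|---|---|
| 40% | 6% |
| 45% | 20% |
| 50% | 44% |
| 55% | 71% |
| 60% | 90% |
| 70% | 99.7% |

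More patients do not help when score 4 dominates: at n = 111 and 60% at score 4, the probability is 98%.

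**Step 3: allowing some score-3 patients.** The first three rows come from 20,000 simulated trials of 32 versus 16 patients with 30% at score 5.

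| Assumed shares at 3 / 4 / 5 | Mean size of lower group | Lower group empty | At least one arm has none |
|---|---|---|---|
| 2 / 68 / 30% | 1.0 | 37% | 86% |
| 5 / 65 / 30% | 2.5 | 8% | 55% |
| 10 / 60 / 30% | 4.9 | 0.6% | 21% |

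With 5% at score 3, the chance that nobody scores 3 is 0.95^48 = 8.5%, which agrees with the simulation. If score 3 is more common, the rule recovers. At 15 / 50 / 35% the lower group has a median of 7 patients and no control patient in about 7% of trials (0.85^16). At 20 / 50 / 30% it has a median of 10 and no control patient in about 3% (0.80^16).

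**Step 4: a fixed cut on the same data.** With 34 patients at 4 and 14 at 5, a cut of 4 or below versus 5 or above gives groups of 34 and 14 and a full-rank design (3 of 3). When the sample median is 4.5 or 5, this cut gives exactly the SAP's own groups.

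**The case against.** The strongest objection is that the deciding input is not in the documents. Entry allows PaO2/FiO2 from above 100 to below 300 mmHg, so high-flow or noninvasive support, and with it score 5, could be common. If half or more score 5, the rule works. This stands, and it is why the point is conditional and shown as a range.

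A reader might infer that the rule works only if at least half of patients score 5 or more. The documents do not support that. The entry route for tachypnoea without oxygen could admit score-3 patients, and step 3 shows that 15 to 20% of them would make a usable lower group. SAP 4.9 makes this unlikely, but only as an expectation. Such a split would also compare patients without oxygen against scores 4 and 5 pooled.

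A reader might also infer that the defect threatens the trial's conclusions or could trigger enrichment by itself. It does not go that far. SAP 7.1.3.1 rests the decision to proceed on the primary analysis alone. An empty subgroup yields no result that could mislead, although a very small one might. Enrichment under SAP 4.7 is discretionary, and the final phase 3 design goes to the competent authority as a protocol amendment with an updated SAP. That update would also be an opportunity to fix the cut for phase 3.

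Nor is baseline severity lost from the analysis. It is a covariate in the phase 2 Cox sensitivity model, and the phase 3 model reuses those covariates. Dyspnea VAS, on a 0 to 100 scale, remains as a related subgroup. Neither replaces the test of interaction with the severity score.

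**Conclusion.** The point holds as a conditional defect in one exploratory subgroup. If more than half of patients score 4 and none score lower, the lower group is empty and the planned interaction test cannot be run. If only a few score 3, the lower group is too small to use and often has no patients in one arm. The conclusion rests on scores concentrating on 4 and 5, which is inferred from eligibility and SAP 4.9, and on an assumed split between them. It needs no extreme assumption: with an even expected split, the rule still fails in 44% of trials of 48 patients. The primary log-rank test and the decision to proceed are unaffected. The practical loss is a pre-specified severity interaction that could otherwise inform phase 3 enrichment.

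**What to change.** Before database lock, replace the median split for this variable in SAP 4.4 with a fixed cut at the scale's own category boundary, score 4 or below versus 5 or above, and use it in both phases. Reversing the tie rule instead (at or below the median versus above it) would only move the problem: with a median of 5 and nobody above, the upper group would be empty.

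The cost is one line of SAP text. The data collected and the Cox model stay the same. There is one downside: the upper group may be small if few patients score 5. If 10% do, it has no control patient in about 19% of trials (0.90^16 = 0.185 with 16 controls). The SAP should therefore also say that group sizes are reported by arm and that the interaction is not interpreted if any cell is empty.

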4.1 General

Appropriate descriptive statistics will be produced, according to the variable:

- for continuous data n , mean, standard deviation (SD), median, Q1-Q3, and range (minimum and maximum) will be presented;
- for categorical data, frequency distributions and percentages will be presented;
- for time-to-event variables, cumulative freedom from event will be evaluated using Kaplan-Meier (KM) method. The degree of uncertainty will be expressed with 95% confidence limits (calculated per the method proposed by Greenwood³). Comparison of curves among arms will be performed with the log-rank test. KM graphs will be presented along with the number of subject-at-risk at exact time points. Subjects who have discontinued/terminated the study without an event will be censored at the date of study discontinuation/termination. Subjects ongoing and who are free from event at the time of database lock (for example at interim analyses) will be censored at the last available date.

Unless otherwise specified, hypothesis testing will be carried out at the $\alpha = 0.050$ level (two-sided) when comparing treatments. For all inferential analyses, p-value will be rounded to three decimal places. Statistical significance will be declared if the rounded p-value will be less than or equal to 0.050. For primary analysis only (section 7.1.2), p-values will be provided at 5th decimal place, in order to compare with efficacy and futility thresholds specified in section 4.5.

Additional post-hoc analysis may be produced to further allow comparison between reparixin and control, according to the results obtained. Any unplanned analyses as well as deviations from the original statistical plan will be clearly documented in the Clinical Study Report.

Derivation rules for efficacy and safety analyses are reported in Table 7 in section 9.

All the data collected and derived in the study will be presented in subject data listings by centre.

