7.1 Analysis of primary efficacy endpoints

7.1.1 Testing strategy and multiplicity adjustment

7.1.1.1 Phase 2

The following null hypothesis is defined: the freedom from composite endpoint (section 3.5.1) in reparixin is lower or equal than control:

$$H_0: T_{\text{REPARIXIN}} \leq T_{\text{CONTROL}}$$

$$H_1: T_{\text{REPARIXIN}} > T_{\text{CONTROL}}$$

where $T_{\text{REPARIXIN}}$ and T_{CONTROL} are the freedoms from composite endpoint for reparixin and standard of care, respectively. The null hypothesis H_0 will be rejected, and preliminary (to be confirmed in phase 3) superiority of reparixin shown if log-rank p-value will be lower than pre-specified threshold, depending at which analysis (interim or final) the test is performed. Thresholds are calculated according to O'Brien-Fleming spending function boundaries and are reported in Table 4.

7.1.1.2 Phase 3

The following null hypothesis is defined: that the freedom from severe composite endpoint (section 3.5.1) in reparixin is lower or equal than control:

$$H_0: \Pi_{\text{REPARIXIN}} \leq \Pi_{\text{CONTROL}}$$

$$H_1: \Pi_{\text{REPARIXIN}} > \Pi_{\text{CONTROL}}$$

where $\Pi_{\text{REPARIXIN}}$ and Π_{CONTROL} are the freedoms from severe composite endpoint for reparixin and standard of care, respectively. The null hypothesis will be rejected, and superiority of reparixin concluded if log-rank p-value will be lower than pre-specified threshold, depending at which analysis (first or second interim or final) the test is performed. Thresholds are calculated according to O'Brien-Fleming spending function boundaries and are reported in Table 5.

Phase 3 null and alternative hypotheses will be tested only if superiority of reparixin is shown in phase 2. Null hypotheses of both phases must be rejected in order to claim superiority of reparixin over standard of care. Consequently, no multiplicity correction of type I error will be applied on primary analyses.

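### SAP 4.4 lets four interaction tests, each at 15% with no joint control, decide which subgroups are analysed; with a uniform effect, about half of trials would open one by chance

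*SAP*

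**What the plan says.** SAP 4.4 introduces its factors with "The following subgroups will be defined based on demographic or baseline characteristics" and lists four: age group, gender, baseline clinical severity score split at the median, and baseline dyspnea VAS split at the median. Each is examined in a "Cox regression model including treatment, subgroup variable and their interaction as covariate". The rule that follows is "Subgroup analysis will be performed if interaction tests are statistically significant at 15% nominal level", and its consequence is "In this case all efficacy endpoints will be analyzed within as described in sections 7.1.2, 7.2.1 and 7.2.2". Those sections contain the log-rank analysis of the composite endpoint, the descriptive tables and the between-arm comparisons of the secondary endpoints at each available time point.

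No adjustment across the four tests is given. The only multiplicity statement, in SAP 7.1.1, concerns the primary hypotheses: "no multiplicity correction of type I error will be applied on primary analyses". SAP 4.4 does not label subgroup results exploratory, whereas protocol 9.4.4 does call tests on exploratory endpoints descriptive.

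SAP 4.7, Table 6, lists population enrichment among the possible phase 3 adaptations, with this trigger: "Based on safety and efficacy results (including subgroup analyses), it may be identified a subset of subjects most likely to benefit from treatment". The same section requires the phase 2 results and the final phase 3 design to go to the competent authority as a protocol amendment before the study proceeds.

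**The concern.** The gate decides which within-subgroup results exist. With 48 patients at 2:1 there are about 16 controls, or roughly eight per level in an even split, so an interaction test responds largely to noise. Four such tests at a lenient level will often yield at least one positive.

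Two things are at stake. First, within-subgroup effects are tabulated only where the arms happened to differ between levels. Those effects are exaggerated by selection, and the matching tables for factors with consistent effects are not produced. Second, if phase 2 succeeds, the people deciding on phase 3 see subgroup evidence already filtered in this way. For a drug that works uniformly, this could argue for a needlessly narrow phase 3 population.

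**Working it through.** The plan states no family-wise figure for these tests, so there is none to reproduce.

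**Inputs**
- Four tests, each at 0.15 (SAP 4.4). SAP 4.4 does not restate sidedness; the general rule in SAP 4.1 is the 0.050 "level (two-sided) when comparing treatments". The family-wise rate under independence does not depend on sidedness.
- 48 patients and 46 events in phase 2, 111 patients in phase 3, 2:1 allocation, exponential times and 21 days of follow-up (SAP 3.2).
- Medians of 2 and 5 days in phase 2 (SAP Table 2), so HR = 2/5 = 0.4.
- Assumptions not in the documents: the correlation between factors, and near-even subgroup splits.

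**1. At least one false trigger, uniform effect, independent tests**

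1 − (1 − 0.15)^4 = 1 − 0.5220 = 0.478. With three usable tests: 1 − 0.85^3 = 0.386.

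**2. Correlated test statistics (multivariate normal, two-sided 15%)**

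| Correlation | At least one false trigger |
|---|---|
| All four, 0.3 | 45% |
| All four, 0.5 | 40% |
| All four, 0.7 | 34% |
| All four, 0.8 | 30% |
| Severity and VAS only, 0.3 to 0.7 | 47% to 45% |

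**3. Simulated trials (Cox Wald interaction tests, no true interaction)**

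Across two sets of simulations at 48 patients (3,000 and 4,000 trials per scenario), with HR 1 or a uniform HR of 0.4 and with independent or moderately correlated factors, at least one test was positive in 51–54% of trials. Monte Carlo error is about √(0.25/3000) = 0.9 percentage points. The result exceeds 48% because each test rejects in about 17–19% of trials at this size, not 15%. At 111 patients, with medians of 3 and 6 days, the figure is 49–51%.

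**4. How large a flagged difference must look**

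With 46 events split evenly, each level has 23. The variance of a log hazard ratio at 2:1 is about 1/(23 × 2/9) = 0.196. The difference between two levels has variance 0.391 and standard error 0.626. The two-sided 15% threshold is 1.44 standard errors: 1.44 × 0.626 = 0.90, and exp(0.90) = 2.5. So any flagged factor shows hazard ratios differing between its levels by a factor of about 2.5 or more, even when the true factor is 1. This is the exaggeration by selection.

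**5. Sensitivity of the gate**

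If the true hazard ratios are 0.4 and 0.8, the log difference is 0.693, or 0.693/0.626 = 1.11 standard errors. The chance of a flag is then about Φ(1.11 − 1.44) + Φ(−1.11 − 1.44) = 0.37 + 0.01 = 0.38. Simulation also gave 38% for the factor concerned.

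**6. Trials that reach phase 3 with a false flag**

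Fixed-design power at HR 0.4 with 46 events: √(46 × 2/9) × 0.916 − 1.96 = 0.97, so power is about 83%. Treating success and a flag as independent and ignoring the interim look, 0.83 × 0.52 = 0.43.

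**The case against.** **A lenient level suits interaction tests.** Their power is low, and SAP 4.4 gives their purpose as deciding whether subgroups need further investigation, which is a screening role. No subgroup claim is planned. This stands as a defence of screening, and choosing between a lenient screen and an ungated display is partly preference. But even at 15% the screen misses the HR 0.4 versus 0.8 contrast in about 62% of trials. Low power is a better reason to show every estimate with its interval than to select tables by p-value.

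**About half is conditional.** This is correct. Strong correlation lowers the figure. The severity score has seven categories with few plausible values in severe inpatients, so its lower group could be very small or empty, leaving three tests.

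**Consistent factors are not necessarily hidden.** All four interaction models are always fitted, and nothing says their results are withheld. Only the within-subgroup analyses are gated.

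**Stronger readings that the documents do not support**
- *A false flag changes phase 3.* Table 6 is permissive ("it may be identified a subset of subjects most likely to benefit from treatment"), rests on safety and efficacy results together, and makes no p-value an automatic trigger. Enrichment also requires a successful phase 2 and an amendment submitted to the competent authority. SAP 7.1.3.1 bases the decision to proceed on the primary analysis alone.
- *An ineffective drug would often be carried forward on a chance subgroup.* Phase 3 requires phase 2 superiority, which SAP 3.2 controls under 0.025 when there is no effect. The enrichment concern therefore applies mainly to an effective drug.
- *Any subgroup result at two-sided 0.05 counts as a finding of benefit.* A two-sided count would include apparent harm. SAP 7.1.2 specifies a one-sided log-rank test, the 0.050 rule in SAP 4.1 applies only where nothing else is specified, and the threshold inside subgroups is not stated.
- *The trial's type I error is inflated.* The primary test does not depend on the subgroup rule.

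**Conclusion.** The point holds as a matter of reporting and multiplicity. With a uniform effect, the plan would open at least one subgroup by chance in about 48% of trials if the tests are independent, and in about 51–54% at 48 patients in simulation. The range is 30–40% if all four statistics are strongly correlated (0.5 to 0.8), and the nominal figure is 38.6% with three tests. These figures assume one endpoint tested once. SAP 4.4 names neither the endpoint nor the phase, and further tests could only raise the rate.

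The consequence is selective and exaggerated subgroup reporting. For a uniformly effective drug, roughly 43% of trials would both succeed in phase 2 and carry a false flag into the phase 3 discussion. The amendment step limits what follows but does not undo the selection in the evidence submitted. The change should be made; the validity of the primary analysis does not depend on it.

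**What to change.** In SAP 4.4:
- Remove the 15% gate.
- Report the primary-endpoint hazard ratio with 95% CI in every level of all four factors, plus each interaction p-value, whatever its value.
- Label these results exploratory and attach no significance statement.
- Delete the extension of within-subgroup testing to all efficacy endpoints.

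Optionally, add to Table 6 that a subgroup or interaction p-value alone is not a basis for enrichment. This only clarifies the present text.

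Tightening the gate is a weaker alternative. Holding the four tests jointly at 15% needs 0.15/4 = 3.75% each, which lowers sensitivity further and still selects what is reported.

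The cost is SAP wording and one forest plot, with no change to sample size, conduct or primary analysis. The sponsor loses within-subgroup tables of secondary endpoints. The estimates shown, from about 46 events, will be imprecise and should be presented as such.
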